# 9.4.8.5 Pregnancy

Details of all pregnancies in female subjects and, if indicated, female partners of male subjects will be collected after the start of IMP and until the final visit.

If a pregnancy is reported, the investigator should inform the sponsor or sponsor's designee within 24 hours of learning of the pregnancy and should follow the procedures outlined in 77.

Pregnancy will not be considered as an adverse event or SAE, but an abnormal outcome (e.g., spontaneous abortion, fetal death, stillbirth, congenital anomalies, ectopic pregnancy) is considered an SAE.

# 9.4.9 Safety review

An ongoing safety review will also be performed. The decision to go to the next dose group will be made by the sponsor. The decision to start dose Group 2 will be based on safety data from at least 5 patients on IFX-1 800 mg, and to start Group 3 on at least 5 patients on IFX-1 1600 mg for at least 1 month.

# 9.5 Immunostaining of biopsy

At baseline, a small biopsy of the target pyoderma gangrenosum ulcer will be taken and sent to a central laboratory.

# 9.6 IFX-1 concentrations

Blood samples will be collected for measurement of plasma concentrations of IFX-1 as specified in the Schedule of Assessments (Section 2). Instructions for the collection and handling of biological samples will be provided by the sponsor or sponsor's designee. The actual date and time (24-hour clock time) of each sample will be recorded.

The plasma concentrations will be used for modeling and simulation.

InflaRx	Clinical Study Protocol,
	Version 4.0 Including Amendment 02, 14 May 2020
IFX-1	IFX-1-P2.7

Each plasma sample will be divided into 2 aliquots (1 sample for concentration measurement, and 1 sample for back-up). Samples collected for analyses of IFX-1 concentrations may also be used to evaluate safety or efficacy aspects related to concerns arising during or after the study.

# 9.7 Immunology and other assessments of blood, ulcer fluid, biopsy and stool samples

Venous blood samples will be collected for the measurement of:

- Anti-drug antibody, antineutrophil cytoplasmic antibody, and antinuclear antibody formation
- Immunology:

Fluid draining from the target ulcer, only if wound is open and liquid is available, will be collected for analysis of:

A biopsy will be collected from the border tissue of the target ulcer for analysis for:

The investigators will be supplied with the necessary sampling tubes **detection** etc.) and instructed to send the samples to a central laboratory from where they will be forwarded to the analyzing laboratories. Further details are given in a laboratory manual.

Remaining samples will be stored for future research at a suitable storage facility (as documented in the trial master file) and analyses may be performed on biomarker variants that are later identified. Samples may be used for research to develop methods, assays, prognostics and/or companion diagnostics related to the disease process and pathways associated with disease state, and/or mechanism of action of the IFX-1.

InflaRx	Clinical Study Protocol,
	Version 4.0 Including Amendment 02, 14 May 2020
IFX-1	IFX-1-P2.7

# 9.8 Genetic evaluations

Genetics are not evaluated in this study.

# 9.9 Health Economics

Health Economics are not evaluated in this study.

# 9.10 Blood Sampling Volumes

The following table gives an estimation of the blood sampling volumes take during the study. These may vary depending on local sampling requirements and techniques.

Reason for sample	Number of samples	Volume per sample (mL)	Total volume (mL)
Clinical chemistry (including serology and pregnancy test) and hematology	6	11.5 mL at Screening 6.5 mL at other visits	44
IFX-1 concentration	6	3	18
Complement factors	7	6	42
Other immunology	7	3	21
QuantiFERON-TB gold test	1	4	4
Anti-drug antibody	7	7 mL at Basaseline, 5 mL at other visits	37
Antineutrophil cytoplasmic antibody and antinuclear antibody	1	7	7
Total:			173

Table 1	Estimated Blood Sampling Volumes
---------	---

The maximum amount of blood collected from each subject over the duration of the study, including any extra assessments that may be required, will not exceed approximately 200 mL. Repeat or unscheduled samples may be taken for safety reasons or for technical issues with the samples.

If values are out of range during screening, a single retest is allowed.

# **10 STATISTICAL CONSIDERATIONS**

# **10.1** Sample Size Determination

The sample size for this study is not based on statistical consideration and no formal sample size estimation has been performed. In total, 18 subjects will be enrolled in the study. It is expected that at least 15 subjects will undergo 3 months treatment (i.e., evaluable). As the

InflaRx	Clinical Study Protocol,
	Version 4.0 Including Amendment 02, 14 May 2020
IFX-1	IFX-1-P2.7

study is a pilot study in the indication of pyoderma gangrenosum and conducted as an open label study, approximately 5 evaluable subjects per initial dosing group seems to be sufficient to explore the safety and tolerability of IFX-1 administered over 189 days to subjects with pyoderma gangrenosum.

# 10.2 Analysis Sets

For purposes of analysis, the following analysis sets are defined:

Analysis Set	Description
Enrolled	All subjects who sign the ICF
Safety Set (SAF)	All subjects who received at least 1 dose of IMP.
Per Protocol Set (PPS)	Subjects who completed at least 3 months of treatment and
	who had no major protocol deviation.

# **10.3** Statistical Analyses

A statistical analysis plan will be developed and finalized before database lock and will describe the analysis sets to be included in the analyses, and procedures for accounting for missing, unused, and spurious data. This section is a summary of the planned statistical analyses of the primary and secondary endpoints.

## 10.3.1 Safety Analyses

The primary objective of this study is to explore the safety of IFX-1 administered in subjects with pyoderma gangrenosum. Safety will be described by the following endpoints:

- TEAEs, defined as adverse events that start at or after the first administration of IMP
- Related TEAEs
- Serious TEAEs
- Adverse events of special interest

TEAEs will be analyzed according to the number and percentage of subjects who had an adverse event as well as the number of TEAEs with the respective MedDRA System Organ Class and Preferred Term. Related TEAEs and serious TEAEs will be analyzed in the same way. Additionally, the number and percentage of subjects with adverse events will be further grouped by severity and relationship. The maximum severity/relationship per subject and preferred term will be counted in these summary tables.

All safety analyses will be performed on the SAF. Analyses will generally be performed for the entire SAF as well as the 3 dosing groups separately. Additional stratifications based on actual dosing and IMP compliance will be defined in the statistical analysis plan.

InflaRx	Clinical Study Protocol,
	Version 4.0 Including Amendment 02, 14 May 2020
IFX-1	IFX-1-P2.7

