# 5.2 Study Sites, Study Subject, and Expected Duration

This study is planned to be a multi-center study with about 18 subjects treated with IMP (IFX-1).

The study start is defined as the date of the first visit of the first subject enrolled (signature of the informed consent form by the first subject), and the end of the study is defined as the date of the last visit of the last subject participating, as recorded in the Case Report Form (CRF).

The estimated recruitment period is approximately 6 to 12 months.

The study duration for an individual subject includes screening (14 days range 7 to 35 days), the treatment period (189 days  $\pm$ 5 days; the last day of dosing of IFX-1 is Day 169), and the observational follow up (60 days  $\pm$ 5 days).

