# 9.4.8.1 Time Period and Frequency for Collecting adverse events and SAE Information

All adverse events and SAEs will be collected from the signing of the informed consent until the final visit at the time points specified in the schedule of assessments (Section 19).

All SAEs will be recorded and reported to the sponsor or sponsor's designee within 24 hours, as indicated in 69. The investigator will submit any updated SAE data to the sponsor or sponsor's designee within 24 hours of it being available.

If the investigator learns of any SAE, including a death, at any time after a subject has been discharged from the study, and he/she considers the event to be reasonably related to the IMP or study participation, the investigator must promptly notify the sponsor or sponsor's designee.

The method of recording, evaluating, and assessing causality of adverse events and SAEs and the procedures for completing and transmitting SAE reports are provided in 69.

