# Appendix 3Adverse Events: Definitions and Procedures for
Recording, Evaluation, Follow-up, and Reporting

#### Definition of an Adverse Event

An adverse event is any untoward medical occurrence in a patient or clinical study subject, whether or not considered related to the IMP.

NOTE: An adverse event can therefore be any unfavorable and unintended sign (including an abnormal laboratory finding), symptom, or disease (new or exacerbated).

Treatment emergent adverse events are adverse events that are temporally associated with the use of IMP.

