**Events Meeting the Adverse Event Definition** 

- Any abnormal laboratory test results (hematology, clinical chemistry, or urinalysis) or other safety assessments (e.g., ECG, radiological scans, vital signs measurements), including those that worsen from baseline, considered clinically significant in the medical and scientific judgment of the investigator (i.e., not related to progression of underlying disease).
- Exacerbation of a chronic or intermittent pre-existing condition including either an increase in frequency and/or intensity of the condition.
- New conditions detected or diagnosed after IMP administration even though it may have been present before the start of the study.
- Signs, symptoms, or the clinical sequelae of a suspected drug-drug interaction.
- Signs, symptoms, or the clinical sequelae of a suspected overdose of either IMP or a concomitant medication. Overdose per se will not be reported as an adverse event/SAE unless it is an intentional overdose taken with possible suicidal/self-harming intent. Such overdoses should be reported regardless of sequelae.
- "Lack of efficacy" or "failure of expected pharmacological action" per se will not be reported as an adverse event or SAE. Such instances will be captured in the efficacy assessments. However, the signs, symptoms, and/or clinical sequelae resulting from lack of efficacy will be reported as adverse event or SAE if they fulfil the definition of an adverse event or SAE.

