#### • Not related (must meet at least one criterion listed below)

This category applies to events that are due to extraneous causes and are not timely related to the administration of the IMP if:

- Event or laboratory test abnormality with a time to administration of the IMP that makes a relationship impossible
- Is most likely explained by concurrent disease or other drugs or chemicals (either pathophysiologically or clinically)

• Has occurred before administration of the IMP in comparable severity and/or frequency

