#### Follow-Up of Adverse Events and SAEs

- The investigator is obligated to perform or arrange for the conduct of supplemental measurements and/or evaluations as medically indicated or as requested by the IRB or regulatory agency to elucidate the nature and/or causality of the adverse event or SAE as fully as possible. This may include additional laboratory tests or investigations, histopathological examinations, or consultation with other health care professionals.
- If a subject dies during participation in the study or during a recognized follow-up period, the investigator will provide copies of any post-mortem findings including histopathology.
- New or updated information will be recorded in the originally completed CRF.
- The investigator will submit any updated SAE data to the sponsor within 24 hours of receipt of the information.

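### Section 10.3.1 defines TEAEs by onset alone, Appendix 3 defines them differently, and no rule covers a screening-onset event that worsens or becomes serious after the first dose

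*Combined protocol and SAP*

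**What the plan says.** Section 10.3.1 gives the only TEAE definition in the analysis section: "TEAEs, defined as adverse events that start at or after the first administration of IMP". It has no clause for worsening. TEAEs, related TEAEs and serious TEAEs, together with adverse events of special interest (AESIs), form the primary endpoint in the Synopsis.

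Appendix 3 (Definition of an Adverse Event) has a second definition: "Treatment emergent adverse events are adverse events that are temporally associated with the use of IMP". This one does not require onset after dosing.

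On collection, section 9.4.8.1 says: "All adverse events and SAEs will be collected from the signing of the informed consent until the final visit". Section 5.2 gives the pre-dose period as "screening (14 days range 7 to 35 days").

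On recording, Appendix 3 (Follow-Up of Adverse Events and SAEs) says: "New or updated information will be recorded in the originally completed CRF".

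Appendix 3 also treats some worsening as an adverse event. The definition covers a "symptom, or disease (new or exacerbated"), and the list of qualifying events includes: "Exacerbation of a chronic or intermittent pre-existing condition including either an increase in frequency and/or intensity of the condition".

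**The concern.** Adverse events with a pre-dose start date can be on record for any subject. Suppose a mild wound infection begins during screening and leads to hospitalization after IFX-1 has started. If the site updates the existing record, the start date stays before the first dose. Under section 10.3.1 the event is then neither a TEAE nor a serious TEAE. The investigator could judge the worsening related to IFX-1 and it would still not be a related TEAE.

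The example fits this population. Exclusion criterion 12 exempts antibiotics for wound superinfection, section 7.2.2 permits oral antibiotics for it on study, and section 3.3.2 lists infection first among the risks that follow from the mode of action.

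The causality text in Appendix 3 already draws the distinction that the TEAE definition lacks. One criterion for calling an event not related is "Has occurred before administration of the IMP in comparable severity and/or frequency", so an event that is worse than before dosing is treated differently there. At stake is whether the primary safety tables show events that became severe or serious on drug.

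**Working it through.** The plan states no figure on this point, so the check is mainly of the text, followed by an illustration of scale.

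**Step 1. Follow a screening-onset event that worsens after dosing.**

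| How the worsening is recorded or classed | Start date | TEAE under 10.3.1? | TEAE under Appendix 3? |
|---|---|---|---|
| Update on the existing record | Before first dose | No | Arguably yes |
| New adverse event for the worsening | After first dose | Yes | Yes |
| Qualifies as an AESI, existing record | Before first dose | No, but enters the primary endpoint as an AESI | Arguably yes |

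No section says which of the first two rows a site should follow. The exacerbation entry in Appendix 3 supports the second row for chronic or intermittent pre-existing conditions. It does not clearly cover an acute event that began in screening, and it does not tell the site to open a new record. The intensity assessment asks for one category per event and no date of change.

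**Step 2. Weight of one missed subject.** Section 7.1.2 gives 6 subjects per group and three groups, so 18 in total.

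- 1/6 = 16.7 percentage points
- 1/18 = 5.6 percentage points

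These are maxima. Section 10.3.1 counts subjects with an event, so the subject is lost from a category only if no other event of theirs falls in it.

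**Step 3. Chance that at least one subject is affected.** The documents give no rate, so assume that a proportion p of subjects has a screening-onset event that worsens on IMP. The chance is 1 − (1 − p)^n.

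| Assumed p | n = 6 | n = 18 |
|---|---|---|
| 2% | 1 − 0.98^6 = 11% | 1 − 0.98^18 = 31% |
| 5% | 1 − 0.95^6 = 27% | 1 − 0.95^18 = 60% |
| 10% | 1 − 0.90^6 = 47% | 1 − 0.90^18 = 85% |

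**Step 4. A ceiling on the share of events involved.** End of treatment is Day 189 and the final visit is 60 days later: 189 + 60 = 249 days. With a constant event rate (assumed) and S days of screening, the share of all events that start before dosing is S/(S + 249).

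- S = 7: 7/256 = 2.7%
- S = 14: 14/263 = 5.3%
- S = 35: 35/284 = 12.3%

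Only the part of this share that later worsens or becomes serious is at issue. Under the constant-rate assumption these figures are therefore upper bounds and do not estimate the loss.

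**The case against.** A reader might infer that such an event can never reach the primary endpoint. The documents do not support that, for four reasons.

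- AESIs are a separate component of the primary endpoint with no onset restriction. They include invasive infection, so the wound-infection example would enter by that route if it became invasive.
- Appendix 3 accepts several kinds of worsening as adverse events in their own right. Besides exacerbations, it lists clinically significant abnormal results that worsen from baseline, and conditions first detected after dosing. Recorded as new events, these satisfy section 10.3.1.
- The rule about the originally completed CRF stands under follow-up and does not forbid a new record.
- The broader Appendix 3 definition could itself be read to cover worsening.

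A reader might also take 2.7% to 12.3% as the proportion of events lost. Most events that start before dosing are rightly excluded under any sensible TEAE definition, so that reading is wrong too.

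It is also fair to say that all SAEs are collected from consent and reported within 24 hours (section 9.4.8.1), that dose-group decisions rest on safety data and not expressly on TEAE tables (section 9.4.9), and that section 10.3 calls itself a summary with a SAP to follow. The documents therefore do not show that safety oversight would miss the event.

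What remains is the gap itself. AESIs do not cover, for example, a non-invasive infection that leads to hospitalization. The second definition adds an inconsistency, and the analysis section uses the narrower of the two. The matters that section 10.3 names for the SAP are analysis sets and missing, unused and spurious data; the TEAE definition is already fixed in 10.3.1. A SAP written later also cannot recover a date of worsening that the CRF never captured.

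**Conclusion.** The point holds in a limited form. The plan has two unreconciled TEAE definitions and no rule for recording a pre-dose event that worsens or becomes serious after the first dose. Under the section 10.3.1 definition such an event can drop out of three of the four primary endpoint components, unless it is entered as a new adverse event or reaches the endpoint as an AESI. The error runs one way: it can lower the counts but not raise them.

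The size cannot be estimated from the documents. At most, each missed subject costs 16.7 points in a group of 6 or 5.6 points of 18. How often this happens depends on an assumed worsening rate and on what sites do in the absence of a rule. With groups this small, and with adverse events also feeding the interim analyses (section 10.3.6), the change is worth making, although the study is exploratory and descriptive.

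**What to change.** 1. Use one TEAE definition in section 10.3.1, Appendix 3 and the SAP: an adverse event with onset at or after the first IMP dose, or one with earlier onset that increases in severity or becomes serious at or after that dose. Remove or align the temporal-association wording in Appendix 3, so that two definitions do not remain.
2. In Appendix 3 and the CRF completion guidance, require either a new adverse event record with its own onset date, or a dated change of severity or seriousness on the existing record, whenever such worsening occurs after the first dose.
3. In the maximum-severity tables, use post-dose severity only. The present rule takes the maximum per subject and preferred term without separating pre-dose from post-dose severity. Once events with pre-dose onset can count, a peak reached in screening could otherwise be tabulated as on-treatment severity.

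The cost is a few sentences in the protocol and SAP, CRF guidance and slightly more recording work at sites. The reported TEAE rate may be slightly higher. The recording rule is the urgent part, because it has to be in place while the data are being collected.

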## **10.3.2 Efficacy Analyses**

The efficacy of IFX-1 for the treatment of skin lesions due to pyoderma gangrenosum is one key secondary objective of this study. Further additional clinical outcome measures will also be investigated. The efficacy endpoints include:

- The responder rate based on the Physician's Global Assessment at Visits V4, V6, V10, and V16 (EOT). Response is defined as a Physician's Global Assessment of ≤3 at the target ulcer
- Time to complete closure of pyoderma gangrenosum target ulcer as assessed by the investigator
- Percentage change in wound area and volume assessed by measurement of photographs of the target ulcer between selected visits (i.e., change between Visits V1 and V4, V1 and V6, V6 and V10, V10 and V16, and V1 and V16)
- Rate of change calculated per day in the area of the target ulcer derived from the photographic measurements
- Number of subjects with a decrease in area of the target ulcer of 50% or more at Visit V16 compared to baseline derived from the photographic measurements
- Number of subjects with a decrease in area of the target ulcer of 100% at Visit V16 compared to baseline derived from the photographic measurements
- A wound healing assessment based on the investigators rating of the target ulcer's erythema and border elevation at Visits V4, V6, V10, and V16 (EOT)

Continuous variables, such as the target ulcer area and ulcer volume, will be analyzed by absolute values and changes from baseline, if applicable. Basic descriptive statistics (e.g., number of observations (n), mean, standard deviation, minimum, median, maximum, lower quartile, upper quartile) will be displayed by visit. All efficacy endpoints will be analyzed descriptively only. Therefore, p-values or confidence intervals resulting from possible statistical models or tests will be interpreted descriptively only. No statements concerning statistical significance are valid.

The number and percentage of subjects in each category will be displayed by visit for categorical or binary variables, such as the responder rate based on the Physician's Global Assessment or the number of subjects with remission.

The time to complete closure will be analyzed with Kaplan-Meier methods using the date of first IMP administration as reference time point. The date of complete closure represents the event date. Subjects who do not experience complete closure of the target ulcer will be censored at the date of their last assessment.

All efficacy analyses will be performed on the SAF and on the PPS. Analyses will generally be performed for the entire study SAF and PPS as well as the 3 dosing groups separately. Additional stratifications based on actual dosing and IMP compliance will be defined in the

InflaRx	Clinical Study Protocol,
	Version 4.0 Including Amendment 02, 14 May 2020
IFX-1	IFX-1-P2.7

statistical analysis plan. Additional further details on the statistical analysis will be specified in the SAP.

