## 7.2.3 **Prohibited Therapy**

The following therapies are prohibited for all subjects from screening until Visit EOT or discontinuation from the study:

- Subject has received a live attenuated vaccine within 3 months prior to screening or plans to receive a live attenuated vaccine during the study or up to 4 weeks after the last study product administration.
- New therapy with biologicals (see 81 for Prohibited Biologics). Biologicals used for an underlying disease at a stable dose may be continued
- Any other systemic medication for pyoderma gangrenosum, including, but not limited to methotrexate, cyclosporine, retinoids, and fumaric acid esters
- Oral or injectable corticosteroids (more than 10 mg prednisone or prednisone equivalent)

- Non-stable, chronic use of high dose oral opioid analgesics
- New prescription topical therapies for pyoderma gangrenosum
- Over-the-counter topical antiseptic washes, creams, ointments, gels, and liquids containing antibacterial agents to treat pyoderma gangrenosum

The following is prohibited for all subjects from screening until Visit Ob2 or discontinuation from the study:

• Any investigational agent

The investigator should contact the sponsor or sponsor's designee if there are any questions regarding prior or concomitant therapy.

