# 8.2 Discontinuation of the IMP

Subjects must be discontinued from treatment with the IMP because of:

- Unacceptable toxicity or TEAE, as determined by the investigator
- Anaphylactic or other serious allergic reaction
- Serious infection, including meningitis and sepsis
- If, in the investigator's opinion, continued administration of IMP could be detrimental to the subject's well-being
- Use of prohibited treatment that in the opinion of the investigator or sponsor or sponsor's designee necessitates the subject being removed
- Biopsy confirmation of any malignancy
- Pregnancy
- Abnormal liver function meeting Hy's Law criteria (62).

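### Section 10.3.2 sets no condition on other pyoderma gangrenosum therapy, so improvement after such therapy would count as IFX-1 efficacy in the safety set

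*Combined protocol and SAP*

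**What the plan says.** **Outcome definitions.** Protocol section 10.3.2 states: "Response is defined as a Physician's Global Assessment of ≤3 at the target ulcer". The 50% and 100% area endpoints rest on the photographic measurement at V16. For time to closure, the closure date is the event, and "Subjects who do not experience complete closure of the target ulcer will be censored at the date of their last assessment". None of these definitions mentions other therapy.

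**Analysis sets.** "All efficacy analyses will be performed on the SAF and on the PPS". Under section 10.2 the SAF is everyone with at least one dose. The PPS needs at least 3 months of treatment and is limited to subjects "who had no major protocol deviation"; the protocol does not say which deviations are major.

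**Other therapy during treatment.** Section 7.2.3 opens its list with "The following therapies are prohibited for all subjects from screening until Visit EOT or discontinuation from the study". The list includes new biologicals, other systemic drugs for PG, corticosteroids above 10 mg prednisone equivalent and new prescription topicals. Section 8.2 makes the consequence conditional. The reason for stopping IMP is "Use of prohibited treatment that in the opinion of the investigator or sponsor or sponsor's designee necessitates the subject being removed".

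**Other therapy after EOT.** Sections 5.1 and 7.3 leave PG treatment after EOT to the investigator. Section 9.1.7 continues the Physician's Global Assessment (PGA), photographs and ulcer assessment at Ob1 (EOT + 30 days) and Ob2 (EOT + 60 days).

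**Left to the SAP.** Section 10.3 assigns to it the analysis sets and "procedures for accounting for missing, unused, and spurious data". Section 10.3.2 adds stratification by actual dosing and IMP compliance, and says "Additional further details on the statistical analysis will be specified in the SAP".

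**The concern.** A second PG drug is most likely to be started in a subject in whom IFX-1 is failing. If that subject then improves, the definitions as stated score a responder or a closed ulcer. There is one treatment and no control arm, so nothing offsets the error, and it runs in the drug's favour. Appendix 3 relies on the efficacy assessments to capture lack of efficacy; a failure that improves after another drug would not be captured there.

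For closure there is a second route that involves no deviation at all. After EOT any PG therapy may be given, the ulcer is still assessed twice, and the closure analysis has no stated end at EOT.

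At stake is how the response and closure figures from a pilot study are read.

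**Working it through.** The plan gives no power, alpha or calculated sample size for these endpoints, so there is no stated figure to reproduce. The group arithmetic is consistent: 3 × 6 = 18 subjects, and 3 × 5 = 15 evaluable.

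**1. Do the rules, followed literally, count such a subject as a success?** Take a dosed subject with no response on IFX-1 who starts cyclosporine for the ulcer.
- 7.2.3: prohibited, so this is a deviation.
- 8.2: IMP stops only if the investigator or sponsor side judges removal necessary. The subject may continue.
- 10.2: stays in the SAF.
- 10.3.2: a PGA of 3 or less at V16 is a response, and a closure is an event.

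The answer is yes.

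**2. Does the PPS repeat correct it?** Only if the use is graded major, and then the subject is dropped, not counted as a failure. Illustration, assuming 6 true responders of 18 and all other subjects in the PPS:

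| Treated failures scored as responders | SAF as written | PPS without them | True rate |
|---|---|---|---|
| 0 | 6/18 = 33.3% | 6/18 = 33.3% | 33.3% |
| 1 | 7/18 = 38.9% | 6/17 = 35.3% | 33.3% |
| 2 | 8/18 = 44.4% | 6/16 = 37.5% | 33.3% |

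With any such subject, both sets lie above the true rate.

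**3. Size per subject.** 1/18 = 5.6 points overall; 1/6 = 16.7 points in a dosing group. The precision is poor anyway: exact 95% intervals are 13.3 to 59.0% for 6/18 and 17.3 to 64.3% for 7/18.

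**4. Expected size under assumptions.** Inflation = (1 − p) × r × s, where p is response without other therapy, r is the share of non-responders given other PG therapy while on IFX-1, and s is the success of that therapy. Section 3.2.2 reports 20 to 90% response for biologicals, used here for s. The documents give no p or r; I assume p = 20 to 50% and r = 10 to 30%.
- Low: 0.5 × 0.1 × 0.2 = 1.0 point.
- Middle (p = 30%, r = 20%, s = 50%): 0.7 × 0.2 × 0.5 = 7.0 points.
- High: 0.8 × 0.3 × 0.9 = 21.6 points.
- With r = 0 the inflation is zero.

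**5. Is there time for it to show?** V7 is Day 57 (7.1.2) and dosing is every 14 days, so V10 = 57 + 42 = Day 99, V11 = Day 113 and V15 = 57 + 112 = Day 169, matching 5.2. V16 is Day 189 (9.1.6). Section 3.2.3 expects an effect after 6 to 8 weeks of treatment; applying that to both IFX-1 and the added drug is an assumption.
- Groups 1 and 2: dose raised at Day 57 and given 6 to 8 weeks, so other therapy starts at Day 99 to 113. Left to V16: 189 − 99 = 90 days (12.9 weeks) to 189 − 113 = 76 days (10.9 weeks).
- Group 3, no dose step: start at Day 57 leaves 189 − 57 = 132 days (18.9 weeks).
- V10: exposed only to therapy started by about Day 57 (99 − 57 = 42 days).
- V6 is Day 43 and V4 is Day 15, so on this assumption they are essentially unexposed.

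**6. Closure after EOT.** Ob1 is Day 189 + 30 = 219 and Ob2 is Day 189 + 60 = 249. An ulcer open at V16, treated with anything after EOT and found closed by Ob2, is an event under 10.3.2. The Kaplan-Meier step is S(t−) divided by the number at risk. With no earlier censoring this is 1/18 = 5.6 points; earlier censoring makes it larger. The PGA and area endpoints end at V16 and are not touched by this route.

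**The case against.** The strongest case against has four parts.

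- **No rescue is planned.** The on-treatment route needs a prohibited drug, a decision to continue IFX-1, and later improvement. The sanctioned path for a failing subject is to stop, complete EOT and only then be treated. This stands: the frequency is unknown and may be zero. It does not apply to closure after EOT, where the other therapy is authorised.
- **The SAP is not in the file.** Section 10.3 calls itself a summary, unused data could be read to include observations after prohibited therapy, and 10.3.2 defers further detail. This stands as a limit: the point concerns the definitions as the protocol states them. However, the topics named do not clearly cover other therapy, and the SAP need only be final before database lock, while interim efficacy summaries in this open-label study come earlier (10.3.6).
- **The PPS and the recorded concomitant therapy allow identification.** Partly right. Subjects can be identified from 7.2.1, but step 2 shows that dropping them does not restore the rate.
- **As-observed results answer a legitimate question.** They do, and should be shown. They describe IFX-1 plus whatever else was given, which is not how a single-arm response rate will be read. Failing subjects for systemic drugs given for another disease would be hard to defend, with inflammatory bowel disease in up to 65% (3.2.2), so the rule should not reach them.

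A reader might infer that the protocol sanctions rescue on IFX-1, that the reported rates will be inflated, or that escalation is compromised. The documents support none of these. Section 7.2.3 prohibits the therapy, no frequency is given, and 9.4.9 bases the start of each next group on safety data.

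**Conclusion.** The point holds for the protocol's definitions. In the SAF, PGA response, 50%/100% area reduction and closure are counted whatever other PG therapy is used. Section 8.2 allows a subject on prohibited PG therapy to remain on IFX-1, so later improvement would be credited to IFX-1. For closure the same applies to therapy allowed after EOT.

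The size is 5.6 points of 18 or 16.7 points of 6 per affected subject. The 1.0 to 21.6 point range rests on assumed response and usage rates and is only illustrative. The effect is on the reading of descriptive secondary figures. The rule is worth settling before results are seen. The point does not concern low-dose steroid or stable biologicals permitted for an underlying disease. Nor does it concern the EOT response or area result of early stoppers, whose EOT visit 5.1 places before other treatment.

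**What to change.** In 10.3.2 and the SAP, for the SAF:

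1. **Trigger.** First use of 7.2.3-prohibited therapy given for PG: new biological, other systemic drug, corticosteroid above 10 mg prednisone equivalent, or new prescription topical. Drugs given for another condition do not trigger the rule; list those cases.
2. **Response and area.** From that date, count later PGA response and 50%/100% area reduction as not achieved.
3. **Closure.** Do not count later closure as an event. Keep subjects who started such therapy before EOT at risk as not closed; censoring them at that start would be informative. A closure documented before such use stays an event.
4. **After EOT.** Either end the closure analysis at EOT, or do not count closures that follow PG therapy started after EOT.
5. **Reporting.** Show as-observed results as a sensitivity analysis, with a dated listing of affected subjects.
6. **PPS.** Name use of prohibited therapy for PG as a major deviation.

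Cost: a few sentences, one listing and one set of sensitivity tables. No new data are needed, since 7.2.1 already records reason for use and start and end dates. The downside is that reported response and closure rates may be lower.
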